Potential risks of this study include 1) inadvertent violation of confidentiality, 2) emotional distress on the part of participants, 3) potential discord during group sessions, given the sensitive topics we discuss. The use of code names and numbers along with other procedures described below are intended to prevent violations of confidentiality. It is important to be aware that participants may be disturbed by sensitive questions raised during data collection and intervention sessions. Questions and discussions regarding drug use, HIV risk behavior including sexual activity, HCV infection, social and family relationships, and discrimination may cause anxiety, anger, suspicions, or other emotions. While this is a predominantly African American sample, there will be some White and Latino participants as well and talking about racism in the group will elicit strong emotions. We welcome homosexual participants and discuss sexuality in groups that may include members who are opposed to homosexuality. Each of these differences has the potential to harm or cause discomfort for the participant or revive psychological dynamics that could threaten to renew old conflicts. We designed *Community Wise* very carefully so that these discussions happen in a safe way, where everyone is encouraged to challenge their own assumptions by analyzing the evidence they have that supports or challenges their positions. This starts with operational components where the intervention is clearly described so that people know what to expect, and ground rules are collaboratively created and enforced during group discussions. In the pilot, there were many instances where the critical questions posed led to a heated dialogue where people were able to express their conflicting views while respecting each other and considering the possibility of changing their point of view. In half of the conditions, we are using licensed facilitators who have a great deal of experience dealing with these sensitive topics and with this marginalized population. The other half will be facilitated by trained peers. We will carefully select peers that show a deep understanding about the challenges of managing a group discussion and we will carefully train them on how to handle potential conflict in the group. The hiring process will be conducted by Drs. [name] and [name], and project director. Facilitators will participate in weekly supervision meetings where we will process any challenges they may experience and sessions will be taped so that we can provide them with feedback on how to improve their performance. In the unlikely event a discussion escalates to the point that it may challenge the safety of the group, or if during a session something happens and the facilitator needs assistance, there are trained NJCRI staff that include licensed clinicians and security in place who can intervene and deflect potential violence. Moreover, during the *Community Wise* pilot study and first year of the current study no adverse events occurring as a result of study participation were observed.

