
Another risk to confidentiality refers to the fact that participants who participate in *Community Wise* groups will learn information about other participants that are shared in the group. Group participants will make a pledge in the first group meeting to maintain confidentiality. While we hope that people will abide by this pledge, it is possible that group members share information about you with other individuals. We disclosed this risk to participants in the informed consent noting this risk for *Community Wise* Groups and research focus groups.

It is possible the NCCB members and group facilitators may know some of the potential clinical trial participants as these individuals live and work in Newark, NJ. Potential clinical trial participants may be clients, family members or friends of any NCCB member. The standard protocol for such situations is to ensure that any NCCB member or group facilitator who has a personal relationship with a potential participant does not interact with that person as part of the study or does not have access to data that identifies their family/friend/ client.

Clinical trial participants will be randomized into the 16 conditions. It is possible that participants may not be randomized into their study condition of choice (e.g., some people prefer peer facilitators while others prefer a licensed clinician). We will clearly explain to participants at the orientation

session that we do not know which condition is the most effective since this research has not been done before. We will describe each condition with a great amount of detail and emphasize the importance to conduct the research properly so that we can find out what is best possible intervention package. We will ensure that prior to consenting to the study, participants will be fully aware that they will not be able to choose what condition they will receive and that they will agree to participate in whatever condition they are randomized to. Those who are set on only participating in a specific condition will be discouraged from entering the study prior to the randomization.

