i. Any research staff member who learns of an adverse event is responsible for reporting the event to the Principal Investigators (PI), who are in turn responsible for discussing the event to make a joint decision about whether the event is serious or non-serious. Events will be categorized as adverse or serious adverse according to NIH guidelines: "Adverse events (AEs) are defined as any untoward medical occurrence that may present itself during treatment or administration of an intervention, and which may or may not have a causal relationship with the treatment. Serious adverse events (SAEs) are defined as any medical occurrence that results in death; is life-threatening; requires inpatient hospitalization or prolongation of existing hospitalization; creates persistent or significant disability/incapacity, or a congenital anomaly/birth defects." As such, adverse events (AEs) occurring during the course of the study will be collected, documented, and reported to the PIs or a designated co-investigator. The occurrence of AEs will be assessed during the intervention phase of the study at baseline and each group visit through clinical observation. Each week a study investigator will review the AE Forms from the previous week for events that were reported as new or continuing. The study investigators will follow all AEs to the point of a satisfactory resolution. A study participant may be withdrawn from the study if the responsible

investigator or group facilitators determine it is the best decision in order to protect the safety of a participant. All AEs will be assessed to determine if they meet criteria for an SAE. If an AE meets criteria for serious adverse event (SAE), as defined by the FDA, they will be systematically evaluated at each clinic visit and treated in a similar fashion as AEs with regards to monitoring and reporting.

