The value of the knowledge to be gained far outweighs the potential risks of participation described above, particularly when considering the precautions we have taken to minimize these risks. As explained earlier in this section, project staff will employ every effort to maintain confidentiality and to minimize any other potential risks; should a serious adverse event occur, it will be reported to the DSMB, Project Officer, funding agencies and the IRBs of the University of Illinois at Urbana-Champaign, NDRI, NJCRI, and Michigan University within 48 hours. Adverse events will be tracked in a database and reviewed at each DSMB meeting. Our CBPR pilot research shows significant community support for this application and community members themselves are committed to assisting us in the successful and safe implementation of this project.

If additional Risk/Benefit information is attached, check here:

23. Is this a multi-center study in which the UIUC investigator is the lead investigator of a multicenter study, or the UIUC is the lead site in a multi-center study. Yes No

If yes, describe the management and communication of information obtained that might be relevant to the protection of subjects, such as: unanticipated problems involving risks to subjects or others, interim results and protocol modifications.

To avoid possible violations of confidentiality, project staff are trained to carefully follow detailed procedures designed to assure that no information about any participant (or others they may mention) will be given to law enforcement, other government agencies, or anyone but research staff. Every member of the research team and all NCCB members will be required to undergo human subject protection training and provide a certificate of completion to the IRB prior to any contact with human subjects. Standards of confidentiality include the use of code numbers and code names for participants and other individuals they may mention. The only place participants' names or other identifying information will appear is on informed consent forms and locator forms (used for follow-up interviews after the baseline). These forms will be kept in a locked filing cabinet at NJCRI, which will be kept separate from data. The Project Director, and [name], a Principal Investigator, are the only people who will have access to the filing cabinet.

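### Adverse events are defined as medical occurrences only, so the non-medical harms the protocol itself names have no stated route to the DSMB

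*Combined protocol and SAP*

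**What the plan says.** Section 20A opens with a numbered list: "Potential risks of this study include 1) inadvertent violation of confidentiality, 2) emotional distress on the part of participants, 3) potential discord during group sessions". It adds a second form of the confidentiality risk, disclosure by fellow group members: "it is possible that group members share information about you with other individuals". Section 20C, item g, accepts that the groups themselves may cause harm.

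Section 20C, item i, gives the classification rule: "Events will be categorized as adverse or serious adverse according to NIH guidelines". The definitions follow. For adverse events: "Adverse events (AEs) are defined as any untoward medical occurrence that may present itself during treatment or administration of an intervention". For serious events: "Serious adverse events (SAEs) are defined as any medical occurrence that results in death; is life-threatening; requires inpatient hospitalization", with further medical outcomes listed after that. On how events are found, the same item says: "The occurrence of AEs will be assessed during the intervention phase of the study at baseline and each group visit through clinical observation".

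Section 22 describes what reaches the board: "Adverse events will be tracked in a database and reviewed at each DSMB meeting".

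**The concern.** The trial tests talk-based groups. Section 20A explains that they deal with drug use, racism, sexuality and discrimination among men with a history of incarceration. The harms such a programme can plausibly cause are mostly social and psychological, and these are the ones section 20A lists. The event definition is a medical one and does not match that list.

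What is at stake is how far the safety record can be interpreted. A report of no adverse events could mean that no breach or altercation occurred, or that such events were never classed as adverse events. The board could not tell which from the AE database. The randomized comparison makes this more important: harm could plausibly differ between peer-led and licensed groups, or with Critical Dialogue, and an independent board is well placed to notice that.

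**Working it through.** The plan gives no figure to reproduce on this point. The check compares texts.

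**Step 1: is there a second definition?** Item i is the only place in the available text that defines an adverse event. The serious-event definition carries the same medical restriction. Nothing widens either one to social, legal or privacy harm, or to psychological harm short of a medical event.

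**Step 2: set each named risk against the definition.**

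| Risk named in section 20A | Within the definition? |
|---|---|
| Confidentiality breach | No |
| Group discord | Only if it leads to injury or another medical event |
| Emotional distress | Only if it amounts to a medical event |

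So two of the three are outside in their ordinary form, and the third is partly outside.

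**Step 3: how events are found.** Item i relies on clinical observation at baseline and at group visits. A disclosure made outside the group would not be observed there.

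**Step 4: follow each other route and see where it ends.**

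- Section 20C, items a, f, g and h: discomfort, disruptive behaviour and harm from groups go to facilitators, the project director, and weekly supervision and staff meetings. None of these items mentions an AE form, the AE database or the DSMB.
- Section 18B, Audio Recordings: safety measures are completed on randomly selected sessions. No link to the DSMB is stated.
- Section 7F: the suicidality screen at baseline and follow-up leads to contact by a clinician. No link to the DSMB is stated.
- Section 20C, item k: the DSMB makes spot checks and preliminary analyses twice a year. No listing of breaches, discord or distress is described.

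None of these texts says that the non-medical harms will be presented to the board.

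**Step 5: exposure, for scale only.** Section 18B gives 48 groups. Over 16 conditions that is 48 / 16 = 3 groups per condition. Sessions summed over the eight component combinations are:

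- participant handouts: 15 + 15 + 15 + 9 + 9 + 9 + 9 + 3 = 84
- section 10 table: 15 + 12 + 12 + 9 + 9 + 6 + 6 + 0 = 69

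Multiplying by 2 facilitator types and 3 groups gives 84 × 6 = 504 and 69 × 6 = 414. The table lists no sessions for the core condition, while the text of section 10 describes three. Using three gives 72 × 6 = 432. The group count is itself uncertain, because 48 groups of at most eleven hold 48 × 11 = 528 men, not 592. These are numbers of sessions. They do not estimate how many harms will occur.

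**The case against.** The strongest reply is that the protocol seems to use the term more broadly elsewhere. Section 20A discusses distress, discord and possible violence, and closes by saying that no adverse events from participation were seen in the pilot or the first study year. As reassurance, that makes most sense if the term covers those harms. The AE form and the session safety measures are not in the available text, and some pages were removed, so they may already ask about such events. This part stands: a reader might infer that staff will leave these harms out and that the AE database will contain none. The documents do not support that. They support only that staff are not required to enter them.

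A second reply is that other safeguards exist. Beyond those in the check above, the baseline survey asks about distress in the past month. Appended site policies call for an incident report after physical confrontation (Integrity House) and an emergency response to bodily harm or homicidal threat (NJCRI). A reader might infer that the harms go unmonitored, or that the board could never see an excess of distress in one condition. Neither follows, since the board analyses study data as well as the AE list. But the site policies do not name the board, the first belongs to an organisation other than the one hosting the groups, and survey items would not show a breach or an altercation.

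A third reply concerns the remedy. Sections 7F and 23 send any adverse event to the IRB and funder within 24 hours, and section 20C, item c, sets 48 hours for reports to the authorities. Putting every verbal dispute or early exit into the AE definition would set off those reports. It would also count as harm the heated dialogue that section 20A describes as expected, perhaps most often in Critical Dialogue groups. This objection is sound, and it is why the fix uses a separate category.

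**Conclusion.** The point holds as a gap between the risks the protocol names and the events its rule requires to be recorded for the board. This is more than missing detail: a stated classification rule, followed as written, omits two of the three named risks and part of the third. The gap is confined to the AE database and the DSMB's review of it, since team-level monitoring exists.

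The conclusion rests on three assumptions: that medical occurrence is read in its ordinary sense, that the AE form adds no broader prompt, and that the removed pages contain no wider definition. No rate of unrecorded harm can be derived from the documents.

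**What to change.** In section 20C, item i, keep the AE and SAE definitions and add a separate category, non-medical study-related harms, logged on the AE form and in the same database. It would cover:

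- any known breach of participant confidentiality;
- any physical altercation or threat of harm in a session;
- any study-related distress that leads to a clinical referral or to withdrawal from the group.

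State that ordinary heated dialogue and leaving a session are not counted. Tabulate the category at each DSMB meeting by component level and facilitator type. State that entries do not by themselves trigger the expedited AE reports. Separately, reconcile the 24-hour limit in sections 7F and 23 with the 48-hour limit in section 20C, item c.

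The cost is a short addition to item i, some extra fields on the form and one table per meeting, with slightly more logging and a higher count of reported events. If sessions have already ended, the safety report should at least say that its AE counts follow a medical definition.

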- *Do not encourage clients to participate in the study, rather mention to them that there is a study going on that they can consider joining if they want to.*
- *Do not answer any of their questions about the study. Simply tell them to call the study number if they have any questions.*

If you have any questions about this request, please contact the project director at the e-mail or phone number below:

[name]

Email: [contact]

[contact]

Approved: *YH*
IRB #: *16574*

Dos and Don'ts of Recruitment

If you do all of these things, you should go into every group with approximately 12 confirmed men in order to get 8 of each.

-Ask for Multiple phone numbers for each participant, not just one. This is more important than family/friend numbers. Some people have different cells that are turned off but will be back on. And house lines too, get as many as possible.

-Ask people when they give a phone number during the phone screening, "is this # you're giving me YOUR number?" If not, def ask for additional numbers!!

- Friend and family numbers are only useful if they are people they live with or see every day so when asking for alternate numbers for family/friends, request this specifically. Anything else is a waste of time.

-on the spreadsheet, keep track of who is friends or related to whom. Some participants are friends or related and this will be very helpful in getting in touch with people.

-If someone sounds very unsure/confused or does not have a phone number or permanent living address, schedule them 5-7 days from the date of their call and do not remind them of their appointment. Some people will surprise you and show up and these people will end up being reliable. For the others it is just a good way of weeding them out without rejecting them.

-For all others, schedule them for the following day or the day after whenever possible. Same day is not good and two days you start losing people. Don't confirm appointments that are within this time frame. People are able to remember without reminders and people who end up needing a lot of reminders end up disappearing and taking up too much time re-scheduling over and over. But if the appointment needs to be more than 2 days away, you should remind people.

-If two people are friends, schedule them back to back so they are more likely to come together and one of them will remember their apt or that they have group.

-Before the suicidal/psychotic questionnaires let people know there is no right or wrong answer and just because they say yes to certain questions doesn't mean they can't participate. Tell them the questions are just to see how they are doing right now. If you don't do this people won't feel comfortable answering honestly and you'll get a lot of conflicting information.

-Stress that the research and intervention are SEPARATE throughout the screenings and baselines.

-For people who miss an appointment with a no call and then call later wanting to reschedule, tell them we have a 2 appt unexcused miss policy and that they will need to call beforehand next time.

-Give yourself a full hour for each screening appt because some people arrive late or early and getting backed up is not fun.

RECEIVED

MAR 21 2016

INST REVIEW BOARD

Approval Date: November 15, 2021
IRB #16574

- Ask people how they are doing, always offer them a comfortable chair, a place to put their bags, lots of snacks and drinks, etc. Make them feel welcome and comfortable.
- Do not take walk-ins. They will usually disappear. Even if you have time to see them, schedule them for the next day if possible. Generally people who insist on being seen the same day are hoping for fast cash and will not be back to attend the groups.
- every time you see someone, give them a bunch of flyers AND business cards and ask them to please tell everyone they know who might be a good fit for the groups. This is how we recruited most people for the pilot.
- Weed people out by their availability during the phone screening so you aren't wasting your time screening someone in person who is not available for the exact group you need to put them in.
- Know the day/time/location of the group by the time you meet with a participant for the first time. Tell them once you what group they were randomized into, date and location of the first group. Give them a business card with this information during the baseline as they leave.
- Ask people if they seem like they might not come to the first group if they are definitely interested. Tell them there are other people waiting to get in if they aren't and it's totally okay if they don't want to come. I found that most people become more committed once they hear they are doing something other people want to do. And if they really don't want to be in it they will tell you.
- If someone is too high to do the baseline or is obviously not taking the questions seriously, waitlist them.
- People call the phone mostly between 8:30am-10:30am. Try to keep this time free during the day to take calls.
- Nobody shows up to 9am appointments so only schedule 10am and after.

Incentive and Study Activities
Condition 1 or 2 – Full Intervention

Session	# of sessions	Length in minutes	Who	Where	How much per session
Phone screen	1	5	Research Assistant	Phone	\$0
Clinical Screen	1	20	Clinician	NJCRI	\$10
Baseline	1	90	Research Assistant	NJCRI	\$20
Community Wise Sessions	15	120	Group facilitators	NJCRI	\$2.50 each attended session (paid at month follow-up)
Follow-up during intervention	5	60	Research Assistant	NJCRI	\$20
Focus group	1	90	Research Assistant	NJCRI	\$20
Total earned over 5 months	---	---	---	---	\$187.50

Group #:

Group Meeting Dates:

Group Meeting Time:

Name of Group Facilitator:

Meeting place address:

Office Phone Number:

Incentive and Study Activities
Condition 3 or 4 – Critical Dialogue (CD) and Quality of Life Wheel (QLW)

Session	# of sessions	Length in minutes	Who	Where	How much per session
Phone screen	1	5	Research Assistant	Phone	\$0
Clinical Screen	1	20	Clinician	NJCRI	\$10
Baseline	1	90	Research Assistant	NJCRI	\$20
Community Wise CD and Core Sessions	9	120	Group facilitators	NJCRI	\$2.50 each attended session (paid at month follow-up)
Community Wise QLW Sessions	6	60	Group facilitators	NJCRI	\$2.50 each attended session (paid at month follow-up)
Follow-ups	5	60	Research Assistant	NJCRI	\$20
Focus group (possible)	1	90	Research Assistant	NJCRI	\$20
Total earned over 5 months	---	---	---	---	\$187.50

Group #:

Group Meeting Dates:

Group Meeting Time:

Name of Group Facilitator:

Meeting place address:

Office Phone Number:

Incentive and Study Activities
Condition 5 or 6 – Critical Dialogue (CD) and Capacity Building Project (CBP)

Session	# of sessions	Length in minutes	Who	Where	How much per session
Phone screen	1	5	Research Assistant	Phone	\$0
Clinical Screen	1	20	Clinician	NJCRI	\$10
Baseline	1	90	Research Assistant	NJCRI	\$20
Community Wise CD and Core Sessions	9	120	Group facilitators	NJCRI	\$2.50 each attended session (paid at month follow-up)
Community Wise CBP Sessions	6	60	Group facilitators	NJCRI	\$2.50 each attended session (paid at month follow-up)
Follow-ups	5	60	Research Assistant	NJCRI	\$20
Focus group (possible)	1	90	Research Assistant	NJCRI	\$20
Total earned over 5 months	---	---	---	---	\$187.50

Group #:

Group Meeting Dates:

Group Meeting Time:

Name of Group Facilitator:

Meeting place address:

Office Phone Number:

**Incentive and Study Activities
Condition 7 or 8 – Critical Dialogue**

Session	# of sessions	Length in minutes	Who	Where	How much per session
Phone screen	1	5	Research Assistant	Phone	\$0
Clinical Screen	1	20	Clinician	NJCRI	\$10
Baseline	1	90	Research Assistant	NJCRI	\$20
Community Wise Sessions	9	120	Group facilitators	NJCRI	\$2.50 each attended session (paid at month follow-up)
Follow-ups	5	60	Research Assistant	NJCRI	\$20
Focus group (possible)	1	90	Research Assistant	NJCRI	\$20
Total earned over 5 months	---	---	---	---	\$172.50

Group #:

Group Meeting Dates:

Group Meeting Time:

Name of Group Facilitator:

Meeting place address:

Office Phone Number:

Incentive and Study Activities

Condition 9 or 10 – Quality of Life Wheel (QLW) and Capacity Building Projects (CBP)

Session	# of sessions	Length in minutes	Who	Where	How much per session
Phone screen	1	5	Research Assistant	Phone	\$0
Clinical Screen	1	20	Clinician	NJCRI	\$10
Baseline	1	90	Research Assistant	NJCRI	\$20
Community Wise Sessions	9	120	Group facilitators	NJCRI	\$2.50 each attended session (paid at month follow-up)
Follow-ups	5	60	Research Assistant	NJCRI	\$20
Focus group (possible)	1	90	Research Assistant	NJCRI	\$20
Total earned over 5 months	---	---	---	---	\$172.50

Group #:

Group Meeting Dates:

Group Meeting Time:

Name of Group Facilitator:

Meeting place address:

Office Phone Number:

**Incentive and Study Activities
Condition 11 or 12- Quality of Life Wheel (QLW)**

Session	# of sessions	Length in minutes	Who	Where	How much per session
Phone screen	1	5	Research Assistant	Phone	\$0
Clinical Screen	1	20	Clinician	NJCRI	\$10
Baseline	1	90	Research Assistant	NJCRI	\$20
Community Wise Core Sessions	3	120	Group facilitators	NJCRI	\$2.50 each attended session (paid at month follow-up)
Community Wise QLW Sessions	6	60	Group facilitators	NJCRI	\$2.50 each attended session (paid at month follow-up)
Follow-ups	5	90	Research Assistant	NJCRI	\$20
Focus group (possible)	1	90	Research Assistant	NJCRI	\$20
Total earned over 5 months	---	---	---	---	\$172.50

Group #:

Group Meeting Dates:

Group Meeting Time:

Name of Group Facilitator:

Meeting place address:

Office Phone Number:

**Incentive and Study Activities
Condition 13 or 14 – Capacity Building Projects (CBP)**

Session	# of sessions	Length in minutes	Who	Where	How much per session
Phone screen	1	5	Research Assistant	Phone	\$0
Clinical Screen	1	20	Clinician	NJCRI	\$10
Baseline	1	90	Research Assistant	NJCRI	\$20
Community Wise Core Sessions	3	120	Group facilitators	NJCRI	\$2.50 each attended session (paid at month follow-up)
Community Wise CBP Sessions	6	60	Group facilitators	NJCRI	\$2.50 each attended session (paid at month follow-up)
Follow-ups	5	60	Research Assistant	NJCRI	\$20
Focus group (possible)	1	90	Research Assistant	NJCRI	\$20
Total earned over 5 months	---	---	---	---	\$172.50

Group #:

Group Meeting Dates:

Group Meeting Time:

Name of Group Facilitator:

Meeting place address:

Office Phone Number:

**Incentive and Study Activities
Condition 15 or 16- Core**

Session	# of sessions	Length in minutes	Who	Where	How much per session
Phone screen	1	5	Research Assistant	Phone	\$0
Clinical Screen	1	20	Clinician	NJCRI	\$10
Baseline	1	90	Research Assistant	NJCRI	\$20
Community Wise Core Sessions	3	120	Group facilitators	NJCRI	\$2.50 each attended session (paid at month follow-up)
Follow-ups	5	90	Research Assistant	NJCRI	\$20
Focus group (possible)	1	90	Research Assistant	NJCRI	\$20
Total earned over 5 months	---	---	---	---	\$157.50

Group #:

Group Meeting Dates:

Group Meeting Time:

Name of Group Facilitator:

Meeting place address:

Office Phone Number:

RECEIVED

OCT 23 2017

UIUC OPRS

OVER 25 YEARS OF PROVIDING HIV AIDS CARE AND TREATMENT TO INDIVIDUALS IN NORTHERN NEW JERSEY IT IS A TEAM EFFORT AND IT IS THIS VERY SYNERGY BETWEEN EACH DEPARTMENT THAT MAKES NJCRI UNIQUE AND A WELCOME OASIS FOR OUR COMMUNITY. WE WILL CONTINUE TO ADAPT AND SUPPORT OUR CLIENTS WITH ESSENTIAL AND INNOVATIVE SERVICES

NJCRI
NORTH JERSEY COMMUNITY RESEARCH INITIATIVE

28 YEARS OF EXPERIENCE **9,500** CLIENTS SERVED A YEAR **25+** GRANT FUNDED PROGRAMS **55** DEDICATED STAFF

[figure not shown]
NJCRI SERVICES

PRIMARY CARE & PHARMACY
SUBSTANCE ABUSE SERVICES
MENTAL HEALTH PSYCHIATRIC
HIV & STI COUNSELING
HIV & STI SCREENINGS
LGBTQ SERVICES
FOOD PANTRY
HEALTH EDUCATION
CLINICAL TRIALS

CLINICAL TRIALS
HOMELESS DROP-IN CENTER
CASE MANAGEMENT
COMMUNITY OUTREACH
TREATMENT ADHERENCE
COMMUNITY HEALTH STUDIES
PRISON DISCHARGE SERVICES
STRANGE EXCHANGE PROGRAM
TRANSPORTATION
ON SITE PHARMACY

ADHERENCE 98% RATE

CRISIS INTERVENTION

- NJCRI Environment
- Word of the Day De-escalation
- Why do we need to talk about this?

CRISIS INTERVENTION

CRISIS LEVEL APPROPRIATE STAFF RESPONSE

ANXIETY Noticeable change or behavior with misdirected directed energy	SUPPORTIVE acknowledge anxiety listen, use empathy ¹ 3-5 non sentences
DEFENSIVE beginning to lose rational thought may act-out	DIRECTIVE set limits that are clear capacity for concise enforceable offer verbally choices ¹ 3-5 words ²
PHYSICAL ACTING-OUT loss of physical and emotional control hurting self, you or others	PHYSICAL INTERVENTION as a last resort ³ Least restrictive technique
TENSION REDUCTION beginning to show guilt memory loss	THERAPEUTIC RAPPORT regain communication open - may cry sleep distinguishing between person and behavior

CRISIS INTERVENTION:

DO'S AND DON'TS

NON VERBAL COMMUNICATION (85%)

A. PERSONAL SPACE (18" to 3' or leg length) size, height, sex appearance, relationship

B. BODY LANGUAGE

Signs when personal space invaded: blushing, tension, position of arms or fists
* WHY THE "L" STANCE?
1. Respect personal space (distance)
2. Less challenging or threatening (position of arms, hands, torso)
3. Increase personal safety (less exposed) better balance

C. PARaverbal communication: how we say it, not what we say

1. Tone of voice-avoid condescending, sarcastic, abusive patronizing
2. Volume
3. Cadence - rate of speech

VERBAL COMMUNICATION

VERBAL ESCALATION CONTINUUM

- 1 QUESTIONING
 - a. seeking information
 - b. challenging authority

- 2 REFUSAL - "no" mode

- 3 VERBAL RELEASE

- 4 INTIMIDATION - threat against self, you or others

- 5 TENSION REDUCTION

APPROPRIATE INTERVENTION LEVEL

Rational response
Redirect, focus on topic

SET LIMITS that are
a. clear - no jargon
b. concise - to the point
c. reasonable - appropriate
d. Avoid power struggle, ally with patient

Allow venting
Isolate
"situation - remove
"individual or audience
Get assistance

Take seriously
Isolate situation
Make environment safe
Get assistance

THERAPEUTIC RAPPORT
Opportunity for learning and growth

TIPS FOR VERBAL INTERVENTION

DO:

- remain calm
- be aware of non-verbals
- isolate situation
- listen - at all stages
- be consistent
- take time

DON'T:

- overreact
- ignore signals
- be threatening
- make false promises

LISTENING SKILLS

1. Remain non-judgmental
2. Don't ignore or fake attention
3. Read between the lines, note mixed messages
4. Reclarify, reflective listening
5. Use silence - shows listening, allows individual time to go on

FACTORS WHICH CAN PRECIPITATE CRISIS IN PATIENTS

- Fear
- Guilt
- Loss of control (health, housing, income)
- Social situation (loss of family, friends, sex partner)
- Holidays, anniversaries
- Staff attitude and behavior
- No one acts out in a vacuum, behavior is reciprocal. If we mirror anxious behavior, we can escalate the situation.
- Psychological -- delusions, hallucinations
- Physiological -- drugs, alcohol, meds, hunger, fatigue, illness

Staff Issues That Affect Work With Clients

- Client's behavior and actions:
 - Attendance
 - Follow through
- Upset with co-workers, supervisors or job in general
- Own personal experience:
 - Substance use recovery
 - View of abstinence vs. harm reduction
 - Years in the field - new or experience
 - Years with same client, same problems
- Expectations of:
 - Client
 - Job
 - Co-workers
 - Personal growth

HOW STAFF CAN COPE WITH FEAR AND ANXIETY

- Know what frightens you (self awareness).
- Fear and frustration often cause of anger.
- Use a team (case conference, individual supervision)
- Know personal safety

STAFF REACTIONS TO FEAR ANXIETY CAN BE

UNPRODUCTIVE

1. Overreact – feelings, actions
2. Freeze
3. Inappropriate behaviors verbally, physically

PRODUCTIVE

1. Increased sensory acuity and awareness
2. Shorter reaction time
 - * Seeking assistance
 - * Creating a safe place

Respect
Privacy, Security and
Confidentiality

Red/Blue Folder

Policy & Procedure

RECEIVED		Issued By:	Policy #
NJCRI [name] Newark, NJ 07103 [contact] [contact] (fax)		[name], L.S.W.	Effective Date:
OCT 23 2017 UIUC OPRS		Prepared By: [name]	Updated 06/14/16
		Approved By:	

Policy Title:

CRISIS INTERVENTION Response to Emergency in the Building

CODE BLUE: will be for medical or mental health emergencies throughout the building.

PURPOSE: To define the procedure to defuse a medical or mental health emergency situation.

POLICY: It will be the policy of NJCRI that by using the over-head page and announcing the code phrase "**Blue Folder**" and the Area (e.g., 2nd floor waiting area, lobby, etc.), would activate the existing response team, who in turn would assist any staff member that may be experiencing a potential medical emergency or mental health crisis with a client or other staff member. The phrase "**Blue Folder**" coupled with the location will instruct/alert security and other key staff members that a response is warranted in the designated area of our building. Emergencies will include, but not be limited to: physical bodily harm, medical emergencies, suicidal or homicidal threat, etc.

